## 11 Statistical Analyses

Summaries will be based on treatment sequence for the following:

- Subject Disposition
- Demographic and Baseline Characteristics
- Prior Medications
- Medical / Surgical History

“Total” columns will be included in these summaries. For all other analyses, summaries will be based on treatment overall and within study periods.

Following conventions will be used for the choice of treatment sequence / group in summaries:

- FAS Population – Planned treatment sequence / group
- Safety Population – Actual treatment sequence / group
- Per-protocol Population – Actual treatment sequence / group

Number of analysis to be done on the primary and secondary endpoints will be confirmed based on subjects exposed to IMP at blinded review meeting.

### 11.1 Subject Disposition

Following categories will be summarised in subject disposition table:

- Subjects in FAS population – frequency (n)
- Subjects in Safety Population – frequency (n) and percentage (%) based on FAS
- Subjects in Per-Protocol Population – frequency (n) and percentage (%) based on FAS
- Subjects completed the study, subjects who attended each visit within each study period - frequency (n) and percentage (%) based on FAS; Early Termination will be summarised in period 2 irrespective of when the subject discontinued from the study.
- Subjects who terminated the study along with reasons - frequency (n) and percentage (%) based on FAS
- Study duration in days – n, mean and standard deviation, median, minimum, maximum

Note that FAS population will be displayed by planned treatment sequence and all other categories will be displayed by actual treatment sequence. Reasons for discontinuation will be sorted by descending order of frequency within the “Total” column.

In DDP: Table 14.1.1

Subject disposition, status of inclusion/exclusion criteria, status of unblinding, subjects excluded from analysis population along with reasons will be listed by subject.

In DDP: Listing 16.2.1.1, Listing 16.2.1.2, Listing 16.2.1.3 and Listing 16.2.3

## 11.2 Protocol Deviations

Number and percentage of subjects with any deviation and number of deviation events will be summarised by treatment within each study period. The same will be sub-classified by category (major/minor) and description as follows:

- Inclusion / Exclusion
- Investigational Product
- Concomitant medications
- Laboratory tests
- Visit Schedule
- Procedures / Tests
- Randomisation
- Safety Reporting
- Protocol Specific Discontinuation Criteria
- Other

Deviation categories will be displayed in the descending order of frequency of total number of deviations in LAT8881 group (both study periods combined). Percentages will be based on FAS population. Protocol deviations occurring between Visit 2 and Visit 3 will be counted in Period 1, and those occurring after Visit 3 will be counted in Period 2.

In DDP: Table 14.1.2

Protocol deviations will be listed by subject.

In DDP: Listing 16.2.2

## 11.3 Demographic and Baseline Characteristics

Demographic and baseline characteristics will be summarised by treatment sequence. Categorical and continuous variables will be provided in the same table. The following variables will be presented: age (years), sex, ethnicity, race, childbearing potential, height (cm), weight (kg) and BMI (kg/m^2). Height, weight and BMI are as reported in screening.

Percentages for childbearing potential will be based only on the female population.

The summary will be repeated for FAS, safety and per protocol populations (as per ICH E3 Guidelines).

In DDP: Table 14.1.3.1 to Table 14.1.3.3

Subject demographics will be listed by subject.

In DDP: Listing 16.2.4.1

### **11.4 Migraine History**

Migraine history will be summarised by treatment sequence. Categorical and continuous variables will be provided in the same table. The following variables will be presented: Time (years) since migraine diagnosis, Average frequency of migraine headaches per month (in last 12 months), Average frequency of migraine headaches per month (in last 12 months) categories ( $\leq 1$ , 2-3, 4-5 and  $>5$ ), Average duration of a migraine headache (hours), Number of subjects experiencing non-migraine headaches, Average frequency of non-migraine headaches per month (in last 12 months), Average frequency of non-migraine headaches per month (in last 12 months) categories ( $<1$ , 2-3, 4-5 and  $>5$ ), Nature of migraines experienced, Average duration of aura (minutes) and Associated symptoms experienced. Number and percentage of subjects with each most troublesome symptom will be summarised by treatment sequence. Symptoms to be included are: nausea, photophobia, phonophobia and other.

Summary will be based on safety population.

In DDP: Table 14.1.4

Migraine history will be listed by subject.

In DDP: Listing 16.2.4.2

### **11.5 Medical/Surgical History**

The number and percentage of subjects with any medical history and number of mentions will be summarised by treatment sequence. The summaries will be provided by system organ class (SOC) and preferred term (PT). System organ class will be displayed in the descending order of frequency of number of mentions in the "Total" column and preferred terms will be displayed in the descending order of frequency within the SOC. Percentages will be based on the safety population. The summary will be repeated for concurrent diseases.

Medical history and concurrent diseases will be classified as mentioned in section 10.8.

In DDP: Table 14.1.5.1, Table 14.1.5.2

Medical history and concurrent diseases will be listed by subject, system organ class and preferred term.

In DDP: Listing 16.2.4.3

### **11.6 Prior and Concomitant Medications**

Medications will be summarised by the study periods below:

- Prior or Pre-Day 1 (Visit 2)
- Pre-IMP: irrespective of the study periods
- Post IMP: LAT8881 60 mg and Placebo

The number and percentage of subjects who have taken any prior medication and number of mentions will be summarised by treatment sequence. Medications will be classified by Therapeutic Main group (ATC Level 2) and Chemical Subgroup (ATC Level 4). The therapeutic main group and chemical substance group will be displayed in the descending order of frequency of total number of mentions. Medications will be coded using the World Health Organisation's Drug-Dictionary (WHODD) version September 2019 or later.

Percentages will be based on the safety population.

The summary will also be presented for concomitant medications by treatment overall and within each study period separately.

Treatment overall: Medications reported before any IMP, irrespective of the study periods will be summarised as 'Pre-IMP'. Medications reported after IMP in period 1 and before IMP in period 2 will be summarised under the treatment assigned at period 1. Medications reported after IMP in period 2 will be summarised under the treatment assigned at period 2. Medications that are ongoing from the previous period and new events will be summarised separately within each treatment period and treatment.

By Study Period: Medications reported post-IMP within each period and treatment will be summarised under the corresponding treatment for that period. Medications that are ongoing from the previous period and new events will be summarised separately within each treatment period and treatment. If a subject has ongoing medication in more than one study period, then the use of that medication is counted in all applicable study periods as 'ongoing'.

Rescue medications and other non-rescue medications will be presented separately. Rescue medications will be presented first followed by other non-rescue medications within the same table.

Percentages will be based on the safety population.

In DDP: Table 14.1.6.1, Table 14.1.6.2 and 14.1.6.3

Prior and Concomitant medications will be listed by subject and therapeutic subgroup. Use of prohibited medications will be recorded as protocol deviations and will be listed in 16.2.2.1.

Rescue medication use over the treatment periods will be listed for each subject separately.

In DDP: Listing 16.2.4.4 and Listing 16.2.4.5

## 11.7 Extent of Exposure

Number and percentage of subjects exposed to IMP and number of subjects not exposed to IMP will be summarised by study period and treatment. Continuous summary statistics will be displayed for

total IMP administered in mg by treatment overall and within each study period. Number and percentage of subjects exposed and not exposed to IMP in any one of the periods or both will also be summarised by study period. The summary will be based on the FAS population.

The same will be repeated for Safety and Per Protocol populations.

In DDP: Table 14.1.7.1, Table 14.1.7.2 and Table 14.1.7.3

IMP administration and compliance data will be listed by treatment sequence, subject and treatment period for FAS population to include the IMP dispensing information.

In DDP: Listing 16.2.5

## **11.8 Efficacy Analyses**

All Efficacy summaries will be based on the Per-Protocol population. The presentation of descriptive summaries for the FAS population will be determined at the blind review meeting prior to database lock based on the difference between the numbers of subjects in each population.

### **11.8.1 Primary Efficacy analyses – NRS Pain Scores**

Migraine pain intensity will be recorded using the NRS in a subject migraine diary at the pre-dose and at 0.5, 1.0, 1.5, 2, 4, 8 and 24 hours post dose. The NRS is an 11-point scale which grades pain from 0 (no pain) to 10 (worst pain imaginable). Pain should reflect the subject's pain at the time of recording.

#### **11.8.1.1 Descriptive summary**

A descriptive summary of NRS pain scores and absolute change from baseline results will be presented by treatment overall and within each study period. Timepoints to be included in this table are: Before IMP was taken (Pre-dose), 30 minutes after IMP taken (t=0.5 hrs), 1 hour after IMP taken (t=1 hr), 1.5 hours after IMP taken (t=1.5 hrs), 2 hours after IMP taken (t=2 hrs), 4 hours after IMP taken (t=4 hrs), 8 hours after IMP taken (t=8 hrs) and 24 hours after IMP taken (t=24 hrs).

#### Difference between treatments:

The difference in absolute NRS pain scores and change from baseline between both treatments will be summarised by timepoint. Timepoints to be included in this table are: Before IMP was taken (Predose), 30 minutes after IMP taken (t=0.5 hrs), 1 hour after IMP taken (t=1 hr), 1.5 hours after IMP taken (t=1.5 hrs), 2 hours after IMP taken (t=2 hrs), 4 hours after IMP taken (t=4 hrs), 8 hours after IMP taken (t=8 hrs) and 24 hours after IMP taken (t=24 hrs). 95% Confidence interval for the difference between treatments will also be provided.

Difference between treatments will be calculated as mentioned in section 10.15.1.

In DDP: Table 14.2.1.1

#### **11.8.1.2 Time-Trend Plots**

Time-trend plots may be created for NRS over time by subject. Each subject will be presented in a separate plot. X-axis will be the timepoint (hours) and Y-axis will be the NRS pain score. Plots will be

grouped by treatment. There may be one or two trend lines per subject based on the number of periods the subject took IMP.

Time trend plots will be created to visualise and compare changes over timepoints in the NRS pain score for subjects in the Per-Protocol population. Mean values of change from baseline within each treatment group along with standard error bars will be plotted on y-axis, and timepoints will be plotted on the x-axis. Treatment groups will be displayed side-by-side in a single page.

Difference in NRS pain scores between both treatments for each subject will also be plotted using time trend plots. Difference between LAT8881 60 mg and Placebo will be plotted in y-axis and timepoints will be plotted in x-axis.

Difference between treatments will be calculated as mentioned in section 10.15.1.

In DDP: Figure 14.2.1.2, Figure 14.2.1.3 and Figure 14.2.1.4

NRS Migraine Pain Scores will be listed by subject.

In DDP: Listing 16.2.6.3

#### 11.8.1.3 Mixed Effect Regression Model for repeated measurements (MMRM)

A mixed effects regression model using a covariance pattern will be fitted to the absolute change from baseline in NRS pain scores at each post-IMP timepoint within each treatment period for the PP population.

The model will have fixed effects for treatment period, timepoint, treatment and the interaction between timepoint and treatment. Baseline pain score within each period will be included as a covariate. A random effect for subject will be included to capture the repeated measures nature of the design.

Least squares means and corresponding 95% confidence intervals (CI) will be presented for the mean changes from baseline for LAT8881, Placebo and the difference between LAT8881 vs. placebo at each timepoint. P-values for testing the null hypothesis that the difference in least squares means between LAT8881 and placebo at each timepoint is 0 will be declared statistically significant if the p-value <0.05.

The covariance pattern will take into account the covariance between observations in different treatment periods and the covariance between observations within the same period (i.e. between timepoints).

```
proc mixed data=; class <subject> <study period>  
<treatment> <timepoint>; model <change> = <baseline> <study  
period> <timepoint>|<treatment>; random <subject>  
<subject>*<period>; lsmeans <treatment>|<timepoint> / pdiff;  
run;
```

In DDP: Tables 14.2.1.5

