14.2 Sample size

No formal statistical sample size estimation has been performed due to the exploratory nature of this study. Rather the sample size is based on clinical and practical considerations.

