## **4.2 Sample Size Justification**

*It is planned to have 20 subjects complete the study, defined as taking one dose of IMP in each treatment period and attending the follow-up (End of study) visit.*

*Assuming up to 20% of subjects do not treat one migraine headache in each treatment period or dropout of the study, 26 subjects will be enrolled in the study.*

[figure not shown]
*If the dropout rate or non-completion rate is higher than anticipated, additional subjects may be enrolled to ensure 20 subjects complete the study.*

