## 8 Statistical Methods

Efficacy endpoints will be summarised in a descriptive manner and analysed using statistical methods described in section 11.8. Changes over time for the primary and secondary efficacy outcomes will be explored using a statistical model as defined in Section 11.8. The level of significance for any statistical tests undertaken will be 0.05 and all tests will be two-sided. Any p-values will be displayed to four decimal places, with p-values less than 0.0001 presented as '<0.0001' and p-values greater than 0.9999 presented as '>0.9999'. All analyses will be done using SAS (version 9.4, SAS Institute Inc., Cary, NC, USA).

Safety endpoints will be summarised in a descriptive manner.

Continuous data will be reported using the following descriptive statistics:

1. Number of observations (n)
2. Mean and standard deviation (SD)
3. Minimum (min) and maximum (max)
4. Median

Minimum and maximum values will be reported to the precision of the endpoint reported with maximum of three decimal places; the mean will be presented with one decimal place more and the standard deviation two decimal places more than the precision of the endpoint reported.

Categorical data will be presented using frequency (n = number of subjects; m = number of events) and percentage (%).

Listings will be provided for all data recorded in the eCRF to study subject profiles. All listings will be sorted by treatment sequence, subject ID, study period and date (if applicable). Unscheduled visit data will only be listed and not included in summaries.

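### The primary mixed model names no degrees-of-freedom method, so under the SAS default the per-timepoint tests use 228 residual df and are slightly anticonservative

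*SAP*

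**What the plan says.** SAP 11.8.1.3 fits one model to change from baseline in pain score at the seven post-dose timepoints of both periods. Its fixed effects are period, timepoint, treatment and timepoint-by-treatment, with the period-specific baseline as covariate. The random effects in the code are subject and subject-by-period, and the code ends with "<subject>*<period>; lsmeans <treatment>|<timepoint> / pdiff". There is no DDFM option and no REPEATED statement.

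The planned inference is by timepoint: "P-values for testing the null hypothesis that the difference in least squares means between LAT8881 and placebo at each timepoint is 0", each called significant below 0.05, with 95% confidence intervals for the same differences. SAP section 8 adds "The level of significance for any statistical tests undertaken will be 0.05 and all tests will be two-sided" and "All analyses will be done using SAS (version 9.4"; it says nothing about degrees of freedom either.

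On size, SAP 4.2 says "It is planned to have 20 subjects complete the study". Protocol 14.2 says "No formal statistical sample size estimation has been performed due to the exploratory nature of this study".

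**The concern.** Each subject-period receives one treatment and yields seven pain scores. Those scores share whatever is particular to that attack, so they are not seven independent pieces of information about treatment. The coded model recognises this in its variance components, through the subject-by-period effect. The reference distribution is a separate matter. If the t quantile is taken at the residual df, the test treats the subject-period variance as almost perfectly known, when it is estimated on few df.

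The consequence is intervals that are too short and p-values that are too small, even if the coded covariance structure is exactly right. These are the only p-values planned for the primary endpoint, so their stated 5% level should be what the code delivers.

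**Working it through.** **Inputs from the documents.** 20 completers (SAP 4.2); 2 periods; 7 post-dose timepoints (SAP 7.1); two-sided 0.05 (SAP 8); the model as coded in SAP 11.8.1.3.

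**Inputs from outside the documents.** (a) With a RANDOM statement and no DDFM option, PROC MIXED uses containment. An effect not contained by name in any random effect then gets the residual df. (b) The within-period correlation ρ is the share of within-subject variance that lies at the subject-period level. The documents give no value; I use 0.2 to 0.9.

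**The plan's own figure.** The SAP states no df. Its one related figure is enrolment: 20/(1 − 0.20) = 25, against 26 stated. That agrees to within one subject and plays no further part.

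**Residual df.** N = 20 × 2 × 7 = 280. The rank of the fixed and random columns together is 40 (subject-periods) + 6 (timepoint) + 6 (timepoint-by-treatment) = 52. Residual df = 280 − 52 = 228. Neither treatment nor timepoint-by-treatment is contained in subject or subject-by-period, so both get 228. The critical t is 1.970.

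**Subject-period df.** 40 subject-periods − 20 subjects − 1 period − 1 treatment − 1 baseline = 17.

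**Variance of a per-timepoint contrast.** It is proportional to MS(subject-period)/7 + (6/7) × MS(residual). With total within-subject variance set to 1:

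- A = (7ρ + 1 − ρ)/7, on 17 df
- B = (6/7)(1 − ρ), on 228 df
- Satterthwaite df = (A + B)² / (A²/17 + B²/228)

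Example, ρ = 0.5: A = 4/7 = 0.571, B = 3/7 = 0.429, A + B = 1. Then df = 1/(0.3265/17 + 0.1837/228) = 50. The critical t is 2.009, and 1 − 1.970/2.009 = 1.9%.

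| ρ | df | critical t | CI too narrow | true error, 20 pairs | true error, 14 pairs |
|---|---|---|---|---|---|
| 0.2 | 127 | 1.979 | 0.4% | 5.1% | 5.1% |
| 0.5 | 50 | 2.009 | 1.9% | 5.4% | 5.6% |
| 0.8 | 25 | 2.061 | 4.4% | 6.0% | 6.5% |
| 0.9 | 20 | 2.084 | 5.4% | 6.2% | 6.9% |

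The error columns come from drawing the two mean squares from their chi-square distributions. For 14 pairs, N = 196, the rank is 28 + 12 = 40, residual df = 156, and subject-period df = 28 − 14 − 3 = 11. In the same draws, a Satterthwaite df gives an error of 5.0% to 5.1%.

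**Second check.** A null simulation of 100,000 trials with 20 subjects, REML estimates and no baseline covariate (so 18 subject-period df) gave 5.0%, 5.4% and 5.8% at ρ = 0.2, 0.5 and 0.8 on 228 df. With Satterthwaite df it gave 4.9% to 5.0%.

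**Other contrasts.** The treatment effect averaged over all timepoints lies wholly in the subject-period stratum. On 17 df its critical t is 2.110, so at 1.970 its interval is 1 − 1.970/2.110 = 6.6% too narrow and its error is 6.5%. Comparisons between timepoints within a period, including the timepoint-by-treatment interaction, are within-period effects for which 228 df is appropriate.

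**Other completion patterns.** With 26 complete pairs the residual and subject-period df are 300 and 23. With 20 pairs plus 6 one-period subjects they are 264 and 17. The gap persists.

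**The case against.** The case on the other side has several parts.

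- **The consequence is small.** At low correlation the error is 5.1%, which is negligible, and at the planned 20 pairs it does not exceed about 6.2%. The study is a proof of concept without a formal sample size, and SAP 8.4 itself urges caution with its tests. This stands, and it sets the weight of the point.
- **The 14-pair case is off plan.** SAP 4.2 allows further enrolment to reach 20 completers. This stands; that column only shows the direction if completion falls short.
- **Other intervals are planned.** SAP 11.8.1.1 provides 95% intervals for the within-subject difference at each timepoint. A standard paired interval on 20 pairs has 19 df and does not depend on the mixed-model default. This stands, but those intervals come without p-values and leave out one-period subjects, whom SAP 8.1 adopts the mixed model in order to include.
- **The code is a template.** It uses placeholders, calls one variable both study period and period, and shows no option for the promised confidence limits. The final program may differ. But no text in the SAP would lead a programmer to set a df method, so the default is what the plan as written yields.

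A reader might infer that every treatment comparison should be on 17 df, or that the 6.5% error applies to the primary tests. Neither follows. The planned contrasts are by timepoint and mix both strata, so their df lies well above 17 over most of the range. The 6.5% belongs to the all-timepoint effect, which the LSMEANS line would print but the text of 11.8.1.3 does not plan to test.

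**Conclusion.** The point holds at modest size. Run as written, the per-timepoint tests and intervals in SAP 11.8.1.3 are anticonservative whenever scores within an attack are positively correlated, as seven ratings of one headache are likely to be. With 20 complete pairs and ρ from 0.2 to 0.9, the excess error is about 0.1 to 1.2 percentage points per test.

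This rests on the SAS containment default, complete diaries, the coded random-intercept structure and the assumed range of ρ. A different covariance structure would change the numbers but not the need to state a df method. The documents do not support reading this as a failure of the primary analysis: the estimates are unaffected, and only a result close to the 0.05 line could change its label.

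**What to change.** Add ddfm=kr (Kenward-Roger), or ddfm=satterthwaite, to the MODEL statement in SAP 11.8.1.3. Name the method in the text of that section and state that it applies whatever covariance structure is finally fitted. Do this before database lock. If the all-timepoint treatment effect is to be reported from the LSMEANS output, say so; the same option covers it.

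The cost is one option and one phrase. With 20 pairs the per-timepoint intervals widen by about 0.4% (1.979/1.970) at ρ = 0.2 and about 5.8% (2.084/1.970) at ρ = 0.9. No data collection or sample size changes.
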